4. At least 3 months post-amputation per physician discretion
5. Residual limb length greater than 6.5 inches in length
6. Able to follow directions and give informed consent on their own or through Legally Authorized Representative.
7. Must be able to ambulate without assistance. An external assistance device such as cane or walker will be permitted.
8. Adequate arterial blood flow of the index stump as evidenced by TcOM > 30 mmHG, measured within the past 12 months.

IV. Exclusion Criteria:

1. Conditions that prevent wearing a prosthetic socket; such as existing scab, ulcer, or keloid scar on amputation stump.
2. Cognitive deficits or mental health problems that would limit ability to consent and participate fully in the study protocol
3. Women who are pregnant or who plan to become pregnant in the near future

V. Study Design:

This study has 3 aims where trans-femoral and trans-tibial amputees will be enrolled.

Subjects enrolled in Aim 1 (N=20) will have one study visit that will take place at The Ohio Willow Wood (OWW).

Subjects enrolled in Aim 2 (N=30) will have a total of 4 visits at baseline, month 1, month 2, and month 3.

Subjects in Aim 3 (120) will be enrolled at Indiana University (n=30 subjects), OWW (n=30), and at Walter Reed National Military Medical Center (WRNMMC) (n=60 subjects) with a total of 3 visits at 0 week (baseline), 0-4 weeks (socket fitting visits), and 16 weeks (final visit).. OWW and Walter Reed National Military Medical Center (WRNMMC) have separate IRB protocol & approval to conduct their part of subject recruitment and study visits. Aims 2 and 3 will not be run concurrently. Subjects enrolled in Aim 2 can participate in Aim 3. Aim 2 studies performed at Ohio State and Indiana University. Aim 2 has enrolled 15 subjects through Ohio State University & OWW (and these 20 subjects have completed their participation in the study) and the data is currently being analyzed to determine if additional subjects are required. If analysis shows sufficient subjects have been enrolled to achieve the study aim, no additional subjects will be enrolled in Aim 2. If there is insufficient data, the remainder of the Aim 2 subjects will be enrolled through OWW under their approved IRB with WIRB. Aim 3 studies performed at IU, OWW and WRNMMC per their approved IRB protocols. The vacuum suspension used for the study is new to all enrolled subjects

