- Hitachi Aloka Ultrasound – A hand held device will be moved gently across the skin and measure your blood flow of deeper skin tissues.
- Skin Temperature-A small tab (small sticker) will be placed on the skin and tell us the temperature of your residual limb
- Surface Electrical Capacitance – Small non-invasive probe place on skin to measure skin hydration
- Trans epidermal water loss measurement (TEWL) – Small non-invasive probe compares relative humidity of skin surface to indicate epidermal barrier function
- Transcutaneous Oxygen Measurement – Small non-invasive probe measures the amount of oxygen released through the skin layer
- This data will be used to determine how socket movement affects the limb health measurements
- The study prosthetist will set vacuum level set to first level
- Digital Image

2. Study Visit 2, 3, 4 (month 1, 2, 3) Subjects will return at 1, 2, and 3 months after study visit 1 where the following research activities will take place:

- Subject will perform seated tasks, standing tasks, and walking on a treadmill task. Skin health measurements will be taken before and after the activity period.
- Hyperspectral Imaging
- Hitachi Aloka Ultrasound
- Skin Temperature
- Surface Electrical Capacitance
- TEWL measurement
- Transcutaneous Oxygen Measurement
- This data will be used to determine how socket movement affects the limb health measurements
- The study prosthetist will set the vacuum level set to the next treatment level except at study visit 4.
- At the end of visit 4, patients will be returned to their standard of care prosthesis. The study prosthetist will be available to review and adjust the fit of their existing prosthesis.
- Digital Image

VIII. Aim 3 (n=30 will be performed at IU under current approved protocol):

Rationale for the amendment: As per the approved DoD proposal, n=60 (n=30 each at IU and Willow wood for Limb Heath analysis, current approved IU IRB protocol) and n=60 subjects were supposed to be completed at Walter Reed (WR) for Functional analysis. We have received a request from WR to perform Functional analysis on the remaining subject that will be enrolled for limb health analysis (this is due to COVID-19 and availability of subjects at WR. The request from WR was also in view of short time line remaining (study end date 09/2021).

After receiving consent, the first enrollment visit will be scheduled for the subjects to see the IU study prosthetist to initiate the “test” socket fitting visits.

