***Note* Study Visit #2A and #2B can be combined and performed in a single study visit upon the discretion of the subject.**

Subjects will begin in their current standard of care prosthesis (the prosthesis worn at time of study enrollment), wherein the following research activities will take place in the following order:

- Subjective questionnaires [Veterans RAND 36-Item Health Survey (VR
- 36, PEQ, Socket Comfort Scores (SCS), and National Institute of Health (NIH) Patient-Reported
- Outcomes Measurement Information System (PROMIS)
- Functional evaluation [Comprehensive High-level Activity Mobility Predictor (CHAMP)]
- Biomechanical evaluation of gait during 6min walking test
 - a. Positioning markers will be placed on the subject while performing the walking assessment to track and describe the movement of the body in three dimensions.
- Repeat SCS outcome

**** applicable to any new enrollments and/or any already enrolled subject completed their limb health part (16 weeks in test sockets followed by 4 weeks in SoC socket as wash off period)**

Following completion of these activities in study visit 2A & B, the subjects will be fitted with the adaptive vacuum suspension by a certified prosthetist that they will wear subsequently wear the device for 16 weeks

The study team will follow up subjects with a weekly phone call to determine the compliance for the use of research socket.

C. **Study Visit #3A – Final Visit (Week 16, +/-2 weeks).** After 16 weeks of wearing the “research” socket the following research activities will take place in the following order:

- Subjects will be asked to walk on a treadmill for 10 mins. The following residual and sound limb health measurements will be taken before and after the activity period with the exception of conducting post-activity ultrasound and digital imaging, is as follows
 - Surface Electrical Capacitance
 - TEWL measurement
 - Hyperspectral Imaging
 - Ultrasound (pre-activity only)
 - Perfusion/ Blood flow
 - Digital Image (pre-activity only)

C.i **Study Visit #3B**— the visit will take place either the same day of Visit 3A or another day within the Week 16, +/-2 weeks based on subject convenience, to repeat research activities previously performed in study visit # 2A

- Subjective questionnaires [Veterans RAND 36-Item Health Survey (VR 36, PEQ, Socket Comfort Scores (SCS), and National Institute of Health (NIH) Patient-Reported Outcomes Measurement Information System (PROMIS)]

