- Functional evaluation [Comprehensive High-level Activity Mobility Predictor (CHAMP)]
- Biomechanical evaluation of gait during 6min walking test
- Repeat SCS outcome

- The subjects will be given a choice to keep the research socket or return to using their original prosthesis as normal. The study prosthetist will be available to review and adjust the fit of their standard of care prosthesis at this time. Note; Due to physical change and limb volume fluctuation over the study period, it is possible that at the end of the study the standard of care prosthesis will not fit your residual limb as it does at the beginning of the study. At the completion of the study it is recommended that the subject follow up with their primary care prosthetist for socket evaluation and fitting.
- Any research-related tests or activities are performed at the expense of the research study and will not be billed to you or your insurance.
- Any non-research related activities, tests, or necessary medical treatment will be provided to you and billed as part of your medical expenses. Costs not covered by your health care insurer will be your responsibility. Also, it is your responsibility to determine the extent of your health care coverage.

Walter Reed National Military Medical Center (WRNMMC) will recruit and enroll 60 subjects with a pin-locking prosthesis and has separate IRB approval to conduct the study. The study visits will be per their approved IRB protocol (see attached).

IX. Study Procedures:

There may be risks that are not known about at this time. Side effects, risks, and discomforts may result from study participation.

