- A. Demographic, medical, and subjective questionnaires: Subjects will be queried on self-reported measures of user comfort and performance. Briefly, four subjective measures will be completed: VR-36, PEQ, SCS, and measures from the NIH PROMIS. The VR-36 was developed from the original RAND version of the Medical Outcomes Study 36-Item Health Survey as a short form functional assessment for veterans. The PEQ is composed of 9 validated scales to measure various aspects of a prosthesis and the users feelings about it. The scales include: Ambulation, Appearance, Frustration, Perceived Response, Residual Limb Health, Social Burden, Sounds, Utility, and Well Being. The SCS is based on a 0-10 numerical scale that assesses comfort rather than pain. The SCS will be administered by asking the participant: "If 0 represents the most uncomfortable socket fit you can imagine and 10 represents the most comfortable socket fit, how would you score the comfort of the socket fit of your artificial limb at the moment?". The NIH developed a system of reliable, precise measures to be used to capture patient-reported physical, mental, and social well-being. The PROMIS tools are aimed at helping clinical researchers most appropriately quantify how a patient is feeling or what they are able to do.

- B. Comprehensive High-level Activity Mobility Predictor (CHAMP) Test: The CHAMP test will be used to assess overall amputee performance and the effect of the socket suspension intervention over time. The conglomeration of clinical assessment tools into the CHAMP was specifically done to measure high-level mobility in service members with a lower limb amputation. CHAMP consists of the Single Leg Stance Test (SLS), the Edgren Side Step Test (ESST), Illinois Agility Test (IAT), and T Test. The SLS measures the time an amputee is able to stand in single support with their hands on their hips and is performed with eyes open and with eyes closed. The ESST measures the ability of the participant to side shuffle back and forth in the layout shown in Figure 20 for 10 seconds. A point is given for each cone passed which is totaled for the 10 seconds. The IAT and T-test requires additional agility and control to navigate the course. Participants will complete the tasks in the following order: SLS, ESST, T-Test, and IAT. To generate a composite CHAMP score, the best times or point for each task is converted to a 0-10 scale following the scoring system. The

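### The Socket Comfort Score is collected by asking the subject in an unmasked comparison, with no rule on who asks, which leaves a risk of courtesy toward the study's own socket

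*Combined protocol and SAP*

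**What the plan says.** Section IX.A describes the instrument: "The SCS is based on a 0-10 numerical scale that assesses comfort rather than pain". It also sets the mode: "The SCS will be administered by asking the participant" a scripted question about how the socket feels at that moment. It names no asker and does not say whether the answer is spoken or written.

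Section VIII (Aim 3) places the ratings. For Visit 2B, "Subjects will begin in their current standard of care prosthesis (the prosthesis worn at time of study enrollment"; the SCS is taken with the questionnaires and again after the gait test ("Repeat SCS outcome"). The final visit comes at the end of the wearing period: "After 16 weeks of wearing the “research” socket the following research activities will take place in the following order". Visit 3B then lists the same two SCS ratings, so there are four per subject.

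On the device and its supplier, section V states that "The vacuum suspension used for the study is new to all enrolled subjects". Section VIII has the research socket fitted within the study: "the first enrollment visit will be scheduled for the subjects to see the IU study prosthetist to initiate the “test” socket fitting visits".

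The protocol contains no provision for masking, for an independent assessor, or for keeping the fitting prosthetist away from outcome collection. The quarterly internal review in section XIII observes visits but does not assign the asker.

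Section XV names CHAMP performance and residual limb health as the Aim 3 model outcomes. It does not name the SCS.

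**The concern.** A comfort rating given in answer to a question from another person can be shaded by politeness toward that person. Here the tie is uneven. The study supplied and adjusted the socket worn up to 3B, whereas the prosthesis rated at 2B is the one the subject was wearing at enrolment. If the asker belongs to the team that supplied the socket, and above all if the asker is the fitter, courtesy could lift the 3B score more than the 2B score. Asking in the same way at both visits would not cancel that difference. Nor would the section XV covariates (age, diabetes status, smoking history), because the shift would move with the device. A reported gain in comfort could then be partly a reporting effect, on the one instrument that the protocol describes as assessing socket comfort.

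**Working it through.** **Text check.** The point needs three conditions.

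1. *The rating is elicited by a person.* Section IX.A has the participant asked. A spoken exchange is the natural reading, but neither the asker nor the response mode is stated.
2. *The subject knows which device is rated.* The 2B rating is made in the subject's own prosthesis and the 3B rating after 16 weeks with a vacuum system that is new to every subject. Masking of the subject is not described and is hardly possible.
3. *Nothing separates fitting from rating.* No such rule appears in sections V, VIII, IX, XIII or XV.

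The second and third conditions are met. The first is met in that the participant is asked, with the details left open.

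**Illustration of size.** The plan has no figure to reproduce: it gives no SD, effect size or power for the SCS.

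Inputs:
- n = 30, the IU allocation for Aim 3 in section VIII. This is an upper bound for the SCS at IU, because Visit 2B applies only to new enrolments and to subjects who have already completed limb health and the 4-week return to standard of care.
- alpha = 0.05, from section XV, taken here as two-sided and without the Holm step.
- Assumed: SD of the paired SCS difference (s) of 2.0 to 2.5 points; reporting shift (b) of 0.5 or 1.0 point; true change zero.

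Formula for a paired t-test: noncentrality d = (b/s)·√n. The probability of significance is P(|T| > c), where T is noncentral t with n−1 degrees of freedom and c is the two-sided critical value.

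For n = 30, c = 2.045:

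| b | s | d | P(significant) |
|---|---|---|---|
| 0 | any | 0 | 5% |
| 0.5 | 2.0 | 0.5/2.0 × 5.477 = 1.369 | 26.3% |
| 0.5 | 2.5 | 0.5/2.5 × 5.477 = 1.095 | 18.5% |
| 1.0 | 2.0 | 2.739 | 75.4% |
| 1.0 | 2.5 | 2.191 | 56.3% |

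Sensitivity of the 0.5-point case, for s = 2.0 and 2.5 respectively:
- n = 15 (assumed), alpha 0.05: 15% and 11%.
- n = 30, alpha 0.01 (an assumed Holm step): 10% and 6%.

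The larger percentages therefore need a large shift, the full n and no multiplicity adjustment together. The paired t-test is also a simplification: section XV plans random-effects regression with covariates and specifies no SCS test.

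**The case against.** The strongest reply is that the documents show only an unnamed asker. A reader might go further and infer that courtesy does inflate the comfort gain, that staff take the rating aloud, that the prosthetist is present, and that only the research socket benefits. None of these is supported:

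- **Inflation as fact.** No shift is reported or estimated anywhere. Only a risk can be stated.
- **Staff, aloud.** Section IX.A says the participant is asked, but it also counts the SCS among measures to be completed, and section VIII lists it with the questionnaires.
- **Prosthetist at the rating.** Section VIII says "The study prosthetist will be available to review and adjust the fit of their standard of care prosthesis at this time", but that sentence follows the last SCS and concerns adjusting the subject's own prosthesis at study end. It does not place the prosthetist at the rating.
- **One direction only.** An unmasked subject might also under-rate the old prosthesis at 2B in anticipation of the new one. Some subjects reach 2B after already wearing the test socket for 16 weeks, so they know the study team by then. The documents do not say who made or last adjusted the standard-of-care prosthesis.

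Two further points stand. The named Aim 3 outcomes do not depend on this rating: CHAMP is timed or counted, and the instrument-based limb-health measures involve no comfort question. And OWW and WRNMMC, 30 + 60 = 90 of the 120 Aim 3 subjects, work under separate protocols that were not available here.

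What the reply does not remove is that the protocol states a mode, asking, when a less bias-prone mode is available at almost no cost.

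**Conclusion.** The concern holds as a risk and is minor. The protocol obtains the SCS by asking the subject in an unmasked comparison of their own prosthesis with a study-supplied socket, without naming the asker or excluding the fitter. Courtesy could raise the research-socket score; upward is the plausible direction, and the size is unknown. The calculation shows that a shift of half a point could matter (about 26% to 19% false significance against a nominal 5%), but only under the assumed SD, n=30 and no Holm adjustment. It is not evidence that such a shift occurs. The finding is limited to the SCS under this IU protocol and leaves the section XV conclusions on CHAMP and instrument-based limb health untouched.

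**What to change.** In section IX.A of this protocol, replace the asking of the SCS with a printed form carrying the same question and its 0-10 scale. The subject marks it privately, before any discussion of fit and without the prosthetist present, in the same way for all four ratings at 2B and 3B. For any subject already rated at 2B, keep the mode used there through 3B and flag the subject in the data. Report the SCS as an unmasked outcome.

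The cost is a one-line form and a sentence of procedure, with no added visit or staff. There are two drawbacks. The response mode will differ between earlier and later subjects, which is why the flag is needed. And private completion reduces the asker's influence but does not remove expectation bias in a subject who knows which socket is being rated.

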On this day, prior to socket fitting activities, the arterial blood flow will be measured on the index stump if not already completed per standard of care within the previous 12 months prior to enrollment for data analysis. Those with an TcOM < 30 mmHG be excluded and no further study activities will be completed. These subjects will be recorded as a screen fail and will not be enrolled.

Others will move forward with socket fitting activities.

- A. **Study Visit #1 - Socket Fitting visits (Week 0 - 4, +/- 2 weeks) – Note: this visit may consist of three (minimum) visits plus socket adjustment visits (as needed by the subject) on separate days (up to 4 weeks)**
 - i) limb shape capture, measurements or tracing
 - ii) diagnostic static fitting and diagnostic dynamic fitting
 - iii) delivery of definitive “research” socket

Once delivery of the definitive research socket has been completed, the subject will be allowed to return for no greater than 4 adjustments (within 0-2 weeks from baseline) to obtain a comfortable fit in order to complete this study. If subject requires more than 4 adjustment visits, the participation from the study will end.

Once the subject is comfortable with the fitting, the date will be noted by the study team as **“research socket use start date”**. From this date, the subject will begin wearing the test socket for next 16 weeks.

- B. **Study Visit #2A - Baseline visit for residual limb health (Week 4, +/- 2 weeks)** Enrollment, after delivery of the definitive research socket and completion of the socket fitting visits, the following research activities will take place to obtain baseline measurements:

- Subjects will be asked to walk on a treadmill for 10 mins. The residual and sound (intact) limb health measurements will be taken before and after the activity period with the exception of conducting post-activity ultrasound and digital imaging. The purpose of acquiring ultrasound and digital imaging is to determine changes in skin structure on a long-term basis; thus, these measurements will only be collected during pre-activity procedures to observe changes in a resting state. The following health measurements will take place:
 - Surface Electrical Capacitance
 - TEWL measurement
 - Hyperspectral Imaging
 - Ultrasound (pre-activity only)
 - Perfusion/ Blood flow
 - Digital Image (pre-activity only)

B.i. Study Visit #2B - Baseline visit for gait assessment (Week 4, +/- 2 weeks)**

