Patients will be informed during the informed consent process (in writing and verbally) that they are free to withdraw from the trial at any time. The Investigator may exercise his medical judgment to terminate a patient's participation in the trial due to clinically relevant changes in any clinical or laboratory parameter. The Sponsor-Investigator also reserves the right to discontinue/terminate the trial at any time.

Discontinuation criteria for individual subjects include: (1) Non-compliance with the inclusion/exclusion criteria, (2) treatment non-compliance, such as use of another socket, (3) withdrawal from the study due to reasons not related to the treatment.

XIII. Procedures for Amendment of Protocol:

Protocol modifications will be approved by the IU IRB prior to implementation and WRNMMC site HQ will be notified if the change is significant or adversely impacts the risk/benefit assessment for the study.

As per IU HRPP guidance on NSR devices reviews trial monitoring, an internal review of data/source verification will be performed and documented on a quarterly basis. The internal reviewer will conduct the following activities: quarterly observation of research recruitment, informed consent process, research activities completed at research study visits, data collection and analysis. The internal review process may meet more frequently as deemed necessary and will be immediately notified of any serious and/or unanticipated event(s) related to procedures of the study. They will review all summary data, overall progress of the study and any individual serious and/or unanticipated event report(s). They do not have any conflicts of interest with the study team and/or protocol. In addition, a Data Safety Monitoring Board (DSMB) will provide independent oversight of the study, and will meet with the PI and research team at the following intervals: (1) prior to enrollment, after enrollment of the first 15 subjects for Aim 2, after enrollment of the first 30 subjects for Aim 3, and after all subjects have been enrolled and within 60 days of completion of the study for both Aims 2 and 3. The DSMB will consist of a physician chairperson, a statistician, and a clinical trialist/ethicist. The Data Safety Monitoring Board will meet at the same intervals separate of the internal research reviewer. .

XIV. Payment:

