All subjects will be compensated \$100 for each of the completed visits. Aim 1 subjects will be compensated \$100 for the completed study visit 1. Aim 2 subjects will have 4 total visits and will be eligible for a maximum of \$400 for completion of all study visits. Aim 3 subjects will have 3 total visits and will be eligible for a maximum of \$450 for the completion of all visits per following schedule: Visit #1 (\$50), Visit #2A & B (\$150, for completing all socket fitting activities

& baseline) and Visit #3A&B (\$250). Subjects will not be paid if any of study visits are not completed.

XV. Statistical Analysis:

Patient demographics and clinical characteristics will be described using frequencies and percentages for categorical data and median and the interquartile range (IQR) for continuous data. In Aim 1, random-effects linear regression will be used to assess the relationship between wave amplitude and distal movement (or lateral shift) controlling for vacuum pressure. Patient ID will be the random-term in the model. In Aim 2, random-effects linear regression will also be used to compare percent change in limb perfusion across adaptive EVS and suction at 12 weeks controlling vacuum pressure and controlling for the baseline EVS and suction values. In Aim 3, a random-effects linear regression model will be used to establish the relationship in amputee performance (as measured by the CHAMP tasks) and residual limb health across EVS and suction and across EVS and pin-locking/lanyard in a cross-over design. The model includes terms for group (EVS vs. suction or EVS vs. pin-locking/lanyard), sequence (EVS to suction vs. suction to EVS or EVS to pin-locking/lanyard vs. pin-locking/lanyard to EVS), and visit (second vs. first). All statistical models will account for the effect of age, diabetes status and smoking history by including them as the covariates in the models. As per need, subjects may be stratified based upon diabetes status and arterial blood flow status. The *p*-values produced in the study will be adjusted using the Holms procedure to control the overall type I error at 0.05 due to the multiple comparisons. All analyses will be run using Stata 13.1, Stata Corporation, College Station, Texas.

XVI. References:

1. Lake, C. The evolution of upper limb prosthetic socket design. *Journal of Prosthetics and Orthotics* 20, 85 (2008).

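### Section XIV pays per completed visit, but its last sentence, read literally, pays nothing if any visit is missed; earned payment should not depend on staying to the end

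*Combined protocol and SAP*

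**What the plan says.** Section XIV (Payment) contains three rules in one paragraph.

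- All subjects receive $100 "for each of the completed visits". For Aim 2, with four visits, the stated maximum is $400.
- Aim 3 subjects have three visits, paid at $50 (Visit 1), $150 (Visit 2A and B, covering the socket fitting and baseline work) and $250 (Visit 3A and B), with a stated maximum of $450.
- The paragraph closes with "Subjects will not be paid if any of study visits are not completed".

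Three provisions elsewhere bear on who might not complete every visit. Section XII tells subjects that "they are free to withdraw from the trial at any time" and lists, among the grounds for discontinuing a subject, "treatment non-compliance, such as use of another socket". Section VIII (Aim 3) says of fitting: "If subject requires more than 4 adjustment visits, the participation from the study will end". The same section describes how adherence is learned: "The study team will follow up subjects with a weekly phone call to determine the compliance for the use of research socket". No section makes an exception to the closing sentence of Section XIV for withdrawal, for participation ended by the study, or for harm from the device.

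**The concern.** The closing sentence cannot be applied together with the rules before it once a subject in Aim 2 or Aim 3 misses a visit. One rule pays for what was completed and the other pays nothing. Two people administering the same text could pay the same subject differently.

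More than tidy drafting is at stake. If money already earned is forfeited on leaving, withdrawal carries a price. Section X lists blisters, and rubbing that leads to ulceration, among the possible discomforts of prosthesis use. A subject with such a problem would have a financial reason to keep going to the final visit. Residual limb health is also an Aim 3 outcome, so the subjects with this reason to continue are those whose condition the study is measuring.

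A second, weaker strand concerns adherence. The only adherence check described is the weekly call, which is self-report. Admitting to use of another socket can lead to discontinuation. If payment is thought to hang on the answer, there is a motive not to give it. Section XV describes no analysis by adherence that would bring socket switching to light.

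**Working it through.** **Inputs**, all from Section XIV: $100 per completed visit; Aim 2 has 4 visits with a maximum of $400; Aim 3 has 3 visits at $50, $150 and $250 with a maximum of $450; nothing is paid if any visit is not completed.

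**Step 1. Reproduce the stated maxima.**

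- Aim 2: 4 × 100 = $400, as stated.
- Aim 3: 50 + 150 + 250 = $450, as stated.
- The opening flat rule applied to Aim 3 gives 3 × 100 = $300, which is not $450. The opening sentence therefore cannot apply to all subjects as it says.

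**Step 2. Pay for a subject who leaves early, under each reading.** Earned pay lost is the per-visit amount minus the literal amount.

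| Subject stops after | Paid per completed visit | Paid under the literal last sentence | Earned pay lost |
|---|---|---|---|
| Aim 3, Visit 1 | $50 | $0 | $50 |
| Aim 3, Visit 2 | 50 + 150 = $200 | $0 | $200 |
| Aim 2, 1 visit | $100 | $0 | $100 |
| Aim 2, 2 visits | $200 | $0 | $200 |
| Aim 2, 3 visits | $300 | $0 | $300 |

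Aim 1 has a single visit, so the two readings agree there.

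**Step 3. How much of the financial pull comes from the last sentence.** Take an Aim 3 subject who leaves during the 16 weeks of wear.

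- Literal reading: forgoes 200 + 250 = $450.
- Milder reading (only the missed visit is unpaid): forgoes $250, which is 250/450 = 56% of the total.
- Part due to the last sentence: 450 − 250 = $200, or 200/450 = 44%.

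The larger part comes from placing $250 on the final visit, and it is present on either reading.

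**Step 4. The subject ended for too many adjustments.** Section VIII counts adjustment visits within Study Visit 1, and Section XIV ties the $150 to completing the fitting work and the baseline. A subject whose participation ends at this stage has at most the $50 for Visit 1 at stake, and only if Visit 1 counts as completed.

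**The case against.** The strongest defence is that the closing sentence is loose drafting for a rule that a missed visit is not paid. A visit-by-visit schedule with a stated maximum has little purpose if payment is all-or-nothing. That reading is plausible and may be what was meant. It does not remove the point, because the sentence says something else and payment is administered from the text.

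Four stronger conclusions are tempting and go further than the documents do.

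- *That Section XIV contradicts Section XII.* Section XII says that subjects may leave at any time. It does not promise that they may do so without loss of payment. The literal rule penalises withdrawal; it does not contradict the words.
- *That an honest answer about another socket costs the subject the final payment.* Section XII does not say whether a discontinued subject attends Visit 3. That link is an assumption.
- *That the rule biases the adherence data or leads subjects to hide skin problems.* It supplies a motive. No figure in the documents shows or sizes an effect, and Section XII lets the investigator end participation for clinically relevant changes.
- *That removing the sentence removes the incentive.* It does not, as Step 3 shows.

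The scope is also limited. Aim 1 is complete. Any further Aim 2 subjects would be enrolled at the manufacturer's site under its own approval. Of the 120 Aim 3 subjects, 30 are studied at Indiana University under this protocol; the other two sites have separate protocols whose payment terms are not visible here. Consent pages are not in the reviewed text, so what subjects were told cannot be checked.

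The mismatch between $300 and $450 is minor: a general sentence followed by a specific schedule that adds up.

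**Conclusion.** The point stands as an internal contradiction in Section XIV with a practical consequence. On the literal reading, an Aim 3 subject who stops after Visit 2 loses $200 already earned, and an Aim 2 subject who stops after three visits loses $300. These amounts assume that a site applies the last sentence as written; on the milder reading they are $0.

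Because the literal rule puts a price on stopping a device whose listed risks include ulceration, and nothing in the documents makes an exception, this is more than a clerical matter and should be corrected. A possible effect on candour in the compliance call should be described only as an inference of unknown size.

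**What to change.** Three changes to Section XIV, carried into the consent form if it repeats the present wording:

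1. Replace the last sentence with: each completed visit is paid as scheduled, regardless of later withdrawal or discontinuation, including when the study ends participation; visits not completed are not paid.
2. Limit the $100-per-visit sentence to Aims 1 and 2, so that the Aim 3 schedule stands alone.
3. State that answers given in the weekly compliance call do not affect payment for any visit attended, including Visit 3A/B.

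No endpoint, visit or clinical rule changes. Compared with literal application, the cost is at most $200 per Aim 3 subject who leaves before the final visit, and up to $300 per Aim 2 subject if more are enrolled. There is a further $250 for any subject who attends Visit 3 after using another socket, but that visit supplies data. For the 30 Indiana University Aim 3 subjects, the extreme case in which all leave after Visit 2 costs 30 × 200 = $6,000. If the sponsor already meant the milder reading, the first change costs nothing.

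The amendment ends forfeiture of earned money. It leaves in place the incentive created by the $250 final payment.
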